### **6.2.1. Preparation and Dispensing**

The study intervention will be dispensed using an IRT drug management system at each vaccination visit (Visits 1 and 3). A qualified staff member will dispense the study intervention via the unique DU number provided. Study intervention should be prepared and dispensed by an appropriately qualified and experienced member of the study staff (eg, physician, nurse, physician's assistant, nurse practitioner, pharmacy assistant/technician, or pharmacist) as allowed by local, state, and institutional guidance.

### **6.3. Measures to Minimize Bias: Randomization and Blinding**

This will be an open-label, single-arm study – participants will not be randomized to vaccine assignment.

#### **6.3.1. Allocation of Study Intervention**

This is an open-label study; however, allocation of vaccine to participants will proceed through the use of an IRT system that is accessible 24 hours a day, 365 days a year. Having logged in, the site personnel (study coordinator or specified designee) will be required to enter or select certain information, including, but not limited to, the user's ID and password, protocol number, participant number, and date of birth of the participant. The site personnel will then be provided with a participant "randomization number" (used as a participant identifier in this study) and DU or container number. The randomization number and the date on which the randomization number was assigned will be recorded on the CRF. Once participant numbers, DU numbers, and randomization numbers have been assigned, they cannot be reassigned. The IRT system will provide a confirmation report containing the participant randomization number and DU or container number assigned. The confirmation report must be stored in the site's files.

The investigator's knowledge of the vaccine assignment should not influence the decision to enroll a particular participant or affect the order in which participants are enrolled.

Study intervention will be dispensed at the study visits summarized in the [SoA](#).

The study-specific IRT reference manual and IP manual will provide the contact information and further details on the use of the IRT system.

### **6.4. Study Intervention Compliance**

Both doses of study intervention will be administered by the appropriately designated study staff at the investigator site.

### **6.5. Concomitant Therapy**

The name and date of administration of any nonstudy vaccine (or allergen immunotherapy) given from the signing of the ICD up to Visit 4 will be recorded on the CRF.

The name, start and stop dates, and route of administration for concomitant medications (prescription and nonprescription) used to treat an AE (excluding events recorded only in the e-diary) from the signing of the ICD to Visit 5 will be recorded in the CRF.

The date and type of any blood transfusion (eg, whole blood, packed cells) received within the 3 months before enrollment through Visit 4 will be recorded on the CRF.

#### **6.5.1. Prohibited During the Study**

1. Nonlive vaccines are not permitted within 14 days before and through 14 days after any study vaccination; live nonstudy vaccines are not permitted within 28 days before and through 28 days after any study vaccination.
2. Intramuscular/sublingual allergen immunotherapy is not permitted within 14 days before and through 14 days after any study vaccination.
3. Systemic (oral, intravenous, or intramuscular) corticosteroid therapy is not permitted within 28 days before through 28 days after any study vaccination.

#### **6.5.2. Permitted During the Study**

1. All treatments that reflect standard of care for immunocompromised participants are permitted.
2. Blood transfusions are permitted during the study.
3. Nonstudy vaccines used in the event of a disease outbreak or pandemic are allowed. In such situations, effort should be made to appropriately plan the administration of study intervention around dosing of the pandemic vaccine.
4. Nonstudy vaccines that are part of recommended immunization schedules are allowed at any time during the study but should not be administered within 14 days (for nonlive vaccines) and 28 days (for live vaccines) of study intervention administration.
5. Antipyretics and other pain medications to treat symptoms associated with study intervention are permitted.
6. Local anesthetic may be applied before blood draw.
7. Topical antibiotics are permitted.
8. Topical and inhaled corticosteroids are permitted.

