baseline 1 month after the second vaccination ranged from 67.4% to 95.0% for the 4 primary MenB test strains (A22, A56, B24, and B44) with a composite response (proportion of participants with hSBA titers  $\geq$  LLOQ for all 4 MenB test strains) of 74.3%. Proportions of participants achieving hSBA titers  $\geq$  LLOQ for 10 secondary strains (A29, A06, A12, A07, A15, A19, B16, B09, B03, and B15) were also high, ranging from 71.1% to 96.8%. These results are comparable to those obtained using the 3-dose schedule in pivotal Phase 3 clinical trials B1971009 and B1971016 in healthy adolescents and young adults, respectively, and support routine use of the 2-dose schedule over the 3-dose schedule outside of the setting of an outbreak. In the setting of an outbreak, 2 doses over a short period of time is desirable to afford more expeditious protection; those 2 doses during the outbreak should be followed by the third dose at 6 months to complete the series.

There is no reason to expect that asplenic individuals' immune responses, as measured by hSBA, would be significantly different from healthy individuals' responses after MenB vaccination, given observations that 2 doses of 4CMenB were similarly immunogenic in this immunocompromised population compared to healthy children. Although there was a trend toward decreased hSBA responses in individuals taking eculizumab who had terminal complement deficiency, the small sample size necessitates further monitoring for vaccine failures. This study is therefore designed to evaluate the safety and immunogenicity of Trumenba when given on the same 2-dose schedule that proved safe and highly immunogenic in healthy adolescents and young adults who participated in Phase 3 Study B1971057.

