**Prior/Concomitant Therapy:**

8. Previous vaccination with any meningococcal serogroup B vaccine.
9. Participants who are receiving any allergen immunotherapy with a nonlicensed product or receiving allergen immunotherapy with a licensed product and are not on stable maintenance doses.
10. Receipt of immunoglobulin infusion or injection during the 42 days preceding enrollment.
11. Current chronic use of systemic antibiotics.
12. Previous receipt or current use of complement inhibitors (eg, eculizumab, ravulizumab).

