4. ANALYSIS SETS (POPULATIONS FOR ANALYSIS)

Data for all participants will be assessed to determine if participants meet the criteria for inclusion in each analysis population prior to releasing the database and classifications will be documented per standard operating procedures.

The analysis populations for immunocompromised participants are defined as below. The age- and sex-matched healthy controls (10 to <26 years) from historical data share the same analysis population definitions. Refer to the Study B1971057 SAP (Version 4, 17 May 2021, Section 4) for the description of analysis sets for the age- and sex-matched healthy controls. In Study B1971057, the study-intervention-allocated population was called the ITT population.

Participant Analysis Set	Description
Enrolled	All participants who sign the ICD, or whose parent(s)/legal guardian(s) sign the ICD.
Study intervention allocated	All participants who are assigned a randomization (participant identification) number in the IRT system.
Evaluable	All participants who were eligible, received all doses of the study intervention according to the vaccine schedule, had blood drawn for assay testing within the required time frames, had valid and determinate assay results for the proposed analysis, and had no major protocol deviations.
ITT	All participants who have at least 1 valid and determinate MnB assay result available at any time point from Day 1 through 1 month after the second vaccination (Visit 4 for this study).
Safety	All enrolled participants who received at least 1 dose of the study intervention and have safety data reported after vaccination.

Defined Population for Analysis	Description
Evaluable immunogenicity	All participants who 
 1. Were eligible through 1 month after Vaccination 2. 2. Received the study intervention at Visit 1 and Visit 3 as randomized. 3. Had blood drawn for assay testing within the required time frames at Visit 1 (before Vaccination 1) and 1 month after Vaccination 2 (28-42 days after Visit 3). 4. Had at least 1 valid and determinate assay result 1 month after Vaccination 2. 5. Received no prohibited vaccines or medications through Visit 4. 6. Had no major protocol deviations through Visit 4.
Vaccination 1 safety	All participants who received the first dose of study intervention at Visit 1 and for whom safety information is available from Visit 1 to prior to Visit 3.

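### Transfusions, and immunoglobulin given after enrolment, could add passive antibody to the Visit 4 serum, and no immunogenicity analysis tests the influence of recipients

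*Protocol*

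**What the plan says.** **Entry.** Protocol 5.2 excludes on "Receipt of immunoglobulin infusion or injection during the 42 days preceding enrollment" (exclusion 10) and on complement inhibitors (exclusion 12). Transfusion is not an exclusion, but its date and type, if "received within the 3 months before enrollment through Visit 4 will be recorded on the CRF" (Protocol 6.5, repeated in SAP 3.4.3), are collected.

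**During the study.** Protocol 6.5.1 prohibits three things around each vaccination: nonstudy vaccines, allergen immunotherapy and, last, systemic corticosteroids ("Systemic (oral, intravenous, or intramuscular) corticosteroid therapy is not permitted within 28 days before through 28 days after any study vaccination"). Immunoglobulin is not listed. Protocol 6.5.2 states "All treatments that reflect standard of care for immunocompromised participants are permitted" and "Blood transfusions are permitted during the study". The only reason to delay a blood draw (5.5.2) is recent systemic antibiotic therapy.

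**Analysis.** Evaluable criterion 5 in SAP Section 4 is "Received no prohibited vaccines or medications through Visit 4". Criterion 6 removes major deviations, and both are settled by clinical review. The only supplementary analysis of the primary proportions is the mITT repeat (SAP 6.1.1.1.2). The only subgroups are sex and race (SAP 6.4).

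**The concern.** The primary objective is to describe the response induced by two doses of vaccine. Protocol 8.1.1 describes the hSBA as measuring antibody in human serum that leads to complement-dependent killing. On that description it does not separate vaccine-induced antibody from antibody received in a blood product. A true non-responder who received donor antibody shortly before Visit 4 could be counted at or above LLOQ.

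The population makes transfusion foreseeable: sickle cell anaemia is a named example of an eligible condition, and the CRF is set up to capture transfusions. The reference group comes from a study of healthy people, so any distortion would probably fall mainly on the immunocompromised group and could make its response look closer to the reference than it is. The baseline percentage, also reported in SAP 6.1.1.1.1, is open to the same question from transfusions before enrolment.

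**Working it through.** **1. Do the rules reach these participants?**

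| Rule | Transfusion before Visit 4 | Immunoglobulin after enrolment |
|---|---|---|
| Exclusions (Protocol 5.2) | not listed | tied to the 42 days before enrolment; nothing later |
| Prohibited list (6.5.1) | not listed | not listed |
| Permitted list (6.5.2) | named | covered if standard of care |
| Blood-draw delay (5.5.2) | no | no |
| Evaluable criterion 5 | not prohibited, so not removed | not prohibited, so not removed |
| Evaluable criterion 6 | not a deviation on its face | not a deviation on its face |
| mITT repeat | recipient is in this set too | recipient is in this set too |

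A recipient who meets the other criteria is in both sets, so comparing the evaluable and mITT results says nothing about these treatments.

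**2. The plan's own precision.** Exact Clopper-Pearson widths at N=50 for proportions 0.5, 0.6, 0.7, 0.8 and 0.9 come to 0.2895, 0.2841, 0.2675, 0.2369 and 0.1849. Protocol Table 7 gives 0.289, 0.284, 0.267, 0.237 and 0.185. These agree to within 0.0005, so the stated precision is correct. The issue is who contributes to the estimate.

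**3. Size of an upward bias.** None of these inputs is in the documents; all are assumptions. Let f be the share exposed near Visit 4, p the true response rate, and q the share of exposed true non-responders lifted to LLOQ or above. Then bias = f × (1 − p) × q.

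| f | q | p = 0.6 | p = 0.8 |
|---|---|---|---|
| 0.10 | 0.25 | 1 point | 0.5 point |
| 0.20 | 0.25 | 2 points | 1 point |
| 0.20 | 0.50 | 4 points | 2 points |
| 0.30 | 0.50 | 6 points | 3 points |
| 0.30 | 1.00 | 12 points | 6 points |

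For example, 0.20 × (1 − 0.8) × 0.50 = 0.02. Over f = 0.10 to 0.30, p = 0.6 to 0.8 and q = 0.25 to 1.00, the range is 0.5 to 12 points.

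A count gives the same ceiling. Suppose 10 of 50 are exposed and 32 of the 40 unexposed respond (80.0%). If all 10 recipients count as responders, the estimate is 42/50 = 84.0%, or 4 points higher, which equals 0.20 × 0.20 × 1.00.

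**4. Precision cost of excluding recipients.** At a response of 0.8 the exact 95% CI width is 0.237 for 40/50, 0.250 for 36/45 and 0.266 for 32/40.

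**5. Complement inhibitors.** Exclusion 12 reads "Previous receipt or current use of complement inhibitors (eg, eculizumab, ravulizumab", with current use included. Sites confirm continued eligibility at Visits 2, 3 and 4, and evaluable criterion 1 requires eligibility through 1 month after Vaccination 2. Read together, these can remove a participant who starts such a drug. Protocol 6.5.2 permits all standard-of-care treatment without exception. The documents do not say which governs.

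**The case against.** The case against is substantial in several places.

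- **Interference is inferred.** Nothing in the documents shows that donor antibody reaches LLOQ on these four strains. Transfusion is only recorded, never an exclusion, and recording does not prove that the plan regards it as interfering. This stands: the effect is possible, not established.
- **The size is assumed.** In healthy recipients 74.3% were at or above LLOQ on all four strains (Protocol 2.2.1), which points to p above 0.6 for single strains. Protocol 4.3 anticipates similar responses here, although 2.2.1 allows that they may be reduced. Participants already on immunoglobulin at intervals of 42 days or less are excluded at entry, so a large f would have to be mostly transfusion. This stands, and favours the lower part of the range.
- **The estimand.** It describes participants who follow the protocol, and permitted care is part of the protocol. This stands as a reason not to remove recipients from the primary set. It does not argue against a sensitivity analysis.
- **The study is descriptive,** with no hypotheses and with groups reported separately. This limits the consequence, but readers will still set the two groups side by side.

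Three stronger readings are tempting but unsupported. First, a reader might infer that no rule removes someone who starts a complement inhibitor; exclusion 12 with evaluable criterion 1 can. Second, a reader might infer that such drugs are shown to lower the result. The protocol says only that "there was a trend toward decreased hSBA responses in individuals taking eculizumab", in people with terminal complement deficiency, with a small sample and a different vaccine. Third, a reader might infer that the transfusion data are used nowhere. A descriptive summary under SAP 6.5.5, whose heading includes nondrug treatments, is possible though its text does not name transfusions. The gap is in the immunogenicity analyses.

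**Conclusion.** The point holds for transfusions and for immunoglobulin given after enrolment. Recipients remain in both immunogenicity sets and no immunogenicity analysis tests their influence, although transfusion date and type are collected through Visit 4. The size is unknown. Under the stated assumptions the upward bias is 0.5 to 12 points, and 1 to 3 points for the three middle cases at a true response of 0.8. The latter is small beside the 0.237 interval width at N=50. The case for acting rests on the low cost of the check, not on a demonstrated bias.

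For complement inhibitors the conclusion is only that exclusion 12 with evaluable criterion 1 conflicts with Protocol 6.5.2 on whether a participant who starts one remains eligible.

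**What to change.** In SAP 6.1.1.1.2, add a prespecified sensitivity analysis of the primary proportions:

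- For 1 month after Vaccination 2, exclude participants with a recorded transfusion, or any recorded immunoglobulin, within a fixed look-back before the Visit 4 draw. Fix and justify the length in advance. The 42 days in exclusion 10 applies to immunoglobulin at entry, and the documents give no basis for carrying it over to transfusion.
- For the baseline percentage, exclude participants transfused in the 3 months before enrolment.
- Leave the primary evaluable set and permitted care unchanged.

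The cost is SAP wording and one extra table, using transfusion data already on the CRF. The table has a smaller n: if 10 of 50 were excluded at a response of 0.8, the interval width would go from 0.237 to 0.266.

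This does not fully cover immunoglobulin. Concomitant medications are recorded only when used to treat an AE (Protocol 6.5 and 8.2), so immunoglobulin or a complement inhibitor given as routine care is not captured now. Testing those fully would need a CRF field, which is a larger change.

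Separately, reconcile Protocol 5.2 (exclusion 12), Protocol 6.5.2 and SAP Section 4 (criterion 1) on a complement inhibitor started during the study, so that evaluable status follows a stated rule.

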#### **6.5.3. Prior Treatment**

1. If the participant is known to have ever received prior vaccination with any of the following vaccines, the name of the vaccine and date of administration will be recorded

on the CRF. It is acceptable to obtain this information from a history obtained verbally from the participant, or via written vaccination record.

- Pneumococcal vaccine
- Meningococcal vaccines containing 1 or more ACWY serogroups

2. The start date and type of blood transfusion (eg, whole blood, packed cells) that immunocompromised participants receive within the 3 months before enrollment in the study will be recorded on the CRF.

## 6.6. Dose Modification

Not applicable.

## 6.7. Intervention After the End of the Study

No intervention will be provided to study participant at the end of the study.

## 7. DISCONTINUATION OF STUDY INTERVENTION AND PARTICIPANT DISCONTINUATION/WITHDRAWAL

### 7.1. Discontinuation of Study Intervention

In rare instances, it may be necessary for a participant to permanently discontinue study intervention (definitive discontinuation). Reasons for definitive discontinuation of study intervention include the following: AEs; parent(s)/legal guardian or participant request; protocol violation.

Note that discontinuation of study intervention does not represent withdrawal from the study. If study intervention is definitively discontinued, the participant will remain in the study to be evaluated for the collection of safety information. See the [SoA](#) for data to be collected at the time of discontinuation of study intervention and follow-up for any further evaluations that need to be completed.

In the event of discontinuation of study intervention, it must be documented on the appropriate CRF/in the medical records whether the participant is discontinuing further receipt of study intervention or also from study procedures, postvaccination study follow-up, and/or future collection of additional information.

Premature termination of this study may occur because of a regulatory authority decision, change in opinion of the IRB/EC, or study intervention safety problems, or at the discretion of Pfizer. If a study is prematurely terminated, Pfizer will promptly notify the investigator. After notification, the investigator must contact all participating participants and the hospital pharmacy (if applicable) immediately. As directed by Pfizer, all study materials must be collected and all CRFs completed to the greatest extent possible.

## 7.2. Participant Discontinuation/Withdrawal From the Study

A participant may withdraw from the study at any time at his/her own request. Reasons for discontinuation from the study include the following:

- Refused further follow-up;
- Lost to follow-up;
- Death;
- Study terminated by sponsor;
- AEs;
- Parent(s)/legal guardian or participant request;
- Protocol violation.

If a participant does not return for a scheduled visit, every effort should be made to contact the participant or the participant's parent(s)/legal guardian. All attempts to contact the participant and information received during contact attempts must be documented in the participant's source document. In any circumstance, every effort should be made to document participant outcome, if possible.

The participant or the participant's parent(s)/legal guardian should be questioned regarding reason for withdrawal. The investigator or his or her designee should capture the reason for withdrawal in the CRF for all participants.

If a participant withdraws from the study, he/she may request destruction of any remaining samples taken and not tested, and the investigator must document any such requests in the site study records and notify the sponsor accordingly.

The participant or the participant's parent(s)/legal guardian should be requested to return for a final visit, if applicable, and the investigator will perform the procedures indicated for the next visit. Any AEs or SAEs that are continuing at the time of withdrawal from the study should be followed until resolution or, in case of permanent impairment, until the condition stabilizes.

A final telephone contact 6 months after the last vaccination ([Section 8.11.5](#)) for the collection of safety information should be completed for all participants who withdraw or have been withdrawn after administration of study intervention, unless consent for further contact has been withdrawn, or the participant is lost to follow-up. Participant withdrawal should be explained in the source documents, and should include whether the withdrawal is only from further receipt of study intervention or also from study procedures and/or postvaccination study follow-up.

If the participant withdraws from the study and his/her parent(s)/legal guardian also withdraws consent (see Section 7.2.1) for disclosure of future information, no further evaluations should be performed and no additional data should be collected. The sponsor may retain and continue to use any data collected before such withdrawal of consent.

Lack of completion of all or any of the withdrawal/early termination procedures will not be viewed as protocol deviations so long as the participant's safety was preserved.

### **7.2.1. Withdrawal of Consent**

Participants who request to discontinue receipt of study intervention will remain in the study and must continue to be followed for protocol-specified follow-up procedures. The only exception to this is when a participant specifically withdraws consent for any further contact with him or her or persons previously authorized by the participant to provide this information. Participants should notify the investigator in writing of the decision to withdraw consent from future follow-up, whenever possible. The withdrawal of consent should be explained in detail in the medical records by the investigator, as to whether the withdrawal is only from further receipt of study intervention or also from study procedures and/or posttreatment study follow-up, and entered on the appropriate CRF page. In the event that vital status (whether the participant is alive or dead) is being measured, publicly available information should be used to determine vital status only as appropriately directed in accordance with local law.

